STUDY PROTOCOL WITH SAP

TITLE

Therapeutic exercise protocol for the prevention of anterior cruciate ligament injuries in female football players with dynamic knee valgus.

DOCUMENT DATE: 30/07/2023

INTRODUCTION

In recent years there has been an exponential growth of women participating in team sports such as football. Around 29 million footballers worldwide are women. In addition, the numbers are constantly growing with an estimated 51% increase in the number of registered players, as is the interest of the female society in this sport¹. The popularity and visibility of women's football is associated with an increase in the number of lower extremity injuries, especially with a high risk of knee injuries. Of all the knee injuries that can occur, women are particularly susceptible to anterior cruciate ligament (ACL) injuries. The ACL plays an important role in knee kinematics². It stabilizes the joint in full extension, prevents rotational loads and anterior displacement of the tibia³. These injuries are a major current problem^{4,5} accounting for 16% to 32% of all injuries and 43% of the injury burden during the sports season⁶. Regardless of their level of participation, female footballers have between 2 and 8 times⁷ times the risk of suffering ACL injuries compared to their male counterparts⁵ performing similar training^{8,9,10}. Injury incidence rates among female soccer players range from 1.1 to 3.1 injuries per 1000 hours of training and from 12.6 to 23.6 injuries per 1000 hours of play over the past decade¹.

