Current training methods include preventive strategies focused on modifying neuromuscular and biomechanical risk factors^{31,32} using non-football-specific tasks such as eccentric exercises or verbal or visual *feedback* combined with plyometric, *core*, balance, resistance or trunk strengthening exercises. These could be the most effective to positively modify the screening, identification and correction of dangerous movement patterns^{1,26} such as DKV during jump-landing tasks^{14,21,31,33,34}. However, no uniform criteria have been established to design a precise intervention protocol, with specific tasks linked to women's football, nor has it been proposed to optimize current programs despite having a high number of injuries associated with DKV^{33,34}. On the other hand, there is no consensus or unification on the establishment of defined parameters regarding the effective dosage of a specific training program, since there is great heterogeneity in terms of the doses and times of the scheduled exercises. These preventive programs are effective in the short term, but it is not equally confirmed whether they produce positive effects in the long term³¹. Current evidence reports that the implementation of specific preventive programs according to the sport practiced is imperative to reduce the incidence of ACL injuries. In addition, in terms of exercise effectiveness, it suggests a 51% reduction in these injuries^{2,20,35,36}.

Based on the review recently published in the journal *Fisioterapia*¹⁶, we proceed to propose, as a continuation of the current research process, an exercise protocol, as well as its dosage in female footballers with DKV, in order to reduce the risk of ACL injuries.

OBJECTIVES AND HYPOTHESES

Main objective

To assess the efficacy of a comprehensive and specific training protocol focused on female players with DKV in preventing ACL injuries.

Specific objectives

1. To investigate the effects of a specific protocol as a preventive method of ACL injuries on the physical performance of female football players.
2. To analyze the injury incidence of ACL among players with DKV in both groups.
3. Check the changes in the neuromuscular control of the knee measured with the "*drop vertical jump test*" (DVJ) in both groups after the corresponding training proposal.
4. To evaluate the biomechanics of landing with jump landing measured with the landing error scoring system (LESS) in participants in both groups.

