the recruitment will be carried out through a direct contact, as an interview, with the coach, the physiotherapist and the physical trainer of the participating teams.

Inclusion and exclusion criteria

The inclusion criteria will be:

- Football players registered and federated in the corresponding team.
- With an age range between 18 and 35 years.
- Minimum experience of one year playing football.
- With the presence of DKV.

The exclusion criteria will be:

- Previously injured subjects of ACL or other knee ligament injury.
- Subjects with a history of lower extremity injuries that have resulted in surgery during the six months prior to the study.
- Players with chronic illnesses that may affect test results.
- Subjects who practice other sports in the professional field.

Study variables and measurements

To record the number of injuries produced among the players of both groups at the end of the study and the frequency of weekly training, an Excel table will be used. The kinetics and kinematics of the lower extremities will also be analyzed with a motion capture system, surface EMG markers and a force platform. The LESS scoring system (Annex V) and the DVJ task will be used to identify the risk of injury during the jump-landing task and the presence of DKV among the players, respectively. In addition, we will measure their pre- and post-intervention satisfaction rates using the SF-12 questionnaire³⁸. Annex VI.

Sample size

An analysis was performed with Epidat 4.2 software to calculate the sample size required in the present study. A comparison of independent means will be performed and a standardized mean difference of 1, a significance level of 0.05, a 95% CI and a power of 90% will be considered, which determines a total sample size of 44 subjects, 22 in each group. It is necessary to consider an abandonment rate, so we will increase the sample by 10%. Therefore, the total sample size will be 48 women, 24 in each study group. Annex VII.

Randomization and blinding

Teams will be randomly assigned to one of the two groups in a simple manner and will be performed once subject selection has been completed. This assignment will be hidden and will be carried out by a person independent of the study. The randomization method will consist of the toss of a coin assigning "heads" to the intervention group and "tails" to the control group.

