First, an invitation will be made to all the players who are part of the teams mentioned above during the 2023-2024 preseason with the aim of starting the intervention during that same season. All respondents will receive a Google survey via WhatsApp. This questionnaire will include questions about the inclusion and exclusion criteria to select the study sample of interest as well as questions about their sports background (position, dominant limb and sports experience); anthropometric measurements (age, height, BMI and weight), which will be provided by the coaches of the selected teams; and aspects related to training (frequency of weekly training and rest period). After completing the survey, three weeks prior to the start of the clinical trial, all players who agree to participate must undergo a final screening to be included in the study. This screening will consist of undergoing a qualitative analysis of the DVJ (Annex VIII), so that, through a simple visual examination, the inclusion of those players who do not present DKV can be ruled out and only those who test positive for DKV can be registered. After selecting the final number of players, a joint talk will be given to both teams to expose the dynamics of the study and the confidentiality of the data. Subsequently, pre-intervention measurements will be carried out by the evaluating physiotherapists to record the initial state of the players. These measures will be: the quantitative analysis of the DVJ, the LESS score, the initial score in the SF-12 scale, the biomechanics of the lower extremities, the muscular activation of the lumbo-pelvic complex and the lower extremity.

During the 12 weeks that the intervention will last, periodic measurements will be made. The last one will take place one month after the end of it. In addition, the players will be asked to refrain from consuming performance stimulants, tobacco or alcohol, non-steroidal anti-inflammatory drugs (NSAIDs) or analgesics 24 hours before each session, as well as strenuous exercise. As a reminder, a WhatsApp will be sent to each athlete the day before each session, indicating the time at which they will be scheduled for training the next day. The appearance of pain during the sessions will not be allowed and, if at any time it appears, the training of the player in question will be stopped immediately and recorded for further analysis.

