The intervention will consist of performing 3 weekly training sessions for 12 weeks to reach a total of 36 sessions of 30-60 minutes each. The days that will be set for training will be Mondays, Wednesdays and Fridays, leaving a rest day between sessions to ensure adequate recovery and quality training. The physical trainers will have to agree so that the training load in both groups is very similar.

Next, we will proceed to detail the intervention that will be carried out in each of the two groups of this clinical trial:

Conventional fitness training group

The players who belong to this group will maintain the usual practice of football training, so no new intervention will be applied.

Training group with a specific ACL injury prevention protocol

This protocol is based on prevention programs that use a multifaceted approach, effective in reducing the risk of ACL injuries compared to those who used only one type of exercise^{14,21,34}. A wide variety of studies defend the importance of working the muscles of the trunk, hip and knee to prevent DKV^{23,28,30}. Therefore, lumbo-pelvic stabilization training (*core* stability) that includes motor stability and strengthening of the gluteal muscles, in addition to strengthening the lower limb itself, will lead to a significant improvement in neuromuscular control of the lower extremities and trunk in addition to producing a significant decrease in DKV and valgus moments^{10,18,20,24,29,30,32}.

The proposed exercise protocol will be designed taking into account the inclusion of three main components. Annex IX:

- Lumbo-pelvic stabilization exercises.
- Lower limb strengthening exercises.
- Integration exercises (plyometrics and balance).

The exercises integrated into the programme will be organised into three phases of implementation:

- **Phase 1** (adaptation - 1st month): Its objective is that the players learn and integrate new patterns while they train.
- **Phase 2** (Proficiency - 2nd month): Aims for players to master new patterns in a controlled environment.
- **Phase 3** (performance - 3rd month): Its objective is to perform exercises in situations as specific as possible and close to the demand and explosiveness of movements typical of the pitch.

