During the execution of all the exercises, verbal and visual inputs will be received, such as the presence of a full-body mirror so that they can correct positions and verbal indications focused on lumbo-pelvic stability and the biomechanics of the lower limb to improve the concentration and motivation of the players during the execution of the scheduled exercises^{9, 12,17,21,33}.

The progression of the exercises will be established by increasing the speed of execution of the same, increasing the complexity of the task to be performed and by promoting neurocognitive implications (for example, counting backwards from 10 to 0 during the execution of the exercises). In addition, compliance with the proposed protocol will be verified through weekly self-reported questionnaires that will be sent via WhatsApp and will be part of the records to be analyzed later by the evaluators.

Expected results

The results we expect to obtain from the intervention group are directly related to the modification of risk factors such as DKV and the decrease in the injury incidence of ACL. It is expected to improve proprioception, body balance and motor control, not only of the lower extremities, but of the entire lumbo-pelvic complex. In addition, it is expected to improve sports performance and ball control on the pitch.

All changes that occur between the players in the intervention group will be measured and recorded. Changes in the neuromuscular control of the knee and the mechanical behavior of the joints proximal and distal to it^{23,28} will be analyzed with a jump-landing test (DVJ)^{19,27,28,32}. Taking advantage of the

previous test, the biomechanics of the jump landing will be evaluated and the risk of non-contact injuries will be identified using the LESS scoring system. In addition, during the execution of the DVJ, the data obtained from the activation of the different pre- and post-intervention muscle groups will be collected and processed with an EMG system^{19,27,29,30}. All these positive changes would imply a lower incidence of injury for the players in the intervention group, as well as higher levels of satisfaction compared to the control group.

Statistical analysis

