First, qualitative variables will be described with frequencies and percentages. For these variables, hypothesis tests will be performed using the Chi-squared test. On the other hand, quantitative variables will be expressed with median and interquartile range (IQR) or with mean, standard deviation and confidence interval (95% CI). It should be verified that the data follow a normal distribution with the Shapiro Wilk test to test this hypothesis. If it were not met, a nonparametric test such as the Mann-Whitney test would be performed. If, on the other hand, it follows a normal distribution, an ANOVA test will be carried out to contrast the mean difference and assess whether or not the results of the clinical trial have been significant. A level of bilateral statistical significance (limit for judging a result as statistically significant) of $\alpha = 0.05$ shall be established for all hypothesis contrasts. The data will be analyzed with the statistical program SPSS.

Budget estimate

The budget available for this study is limited to material costs, since we have the collaboration of the team of physiotherapists from several clinics in the province of Alicante. Therefore, we will select, from among those who are willing to collaborate, both the evaluating and sports physiotherapists for the study. In addition, they will provide much of the materials needed to conduct the study. If, on the other hand, the collaborating clinics did not have all the necessary material, the cost of more specific devices

such as the mDurance surface EMG (€ 5,500 approx.) and the BMS force platform (€ 3,000 approx.) should be included in the budget.

FUTURE EXPECTATIONS OF THE STUDY

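### Match time is not among the listed data, so a difference in match exposure between the two clubs could mimic or hide a programme effect on ACL injury

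*Combined protocol and SAP*

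**What the plan says.** Specific objective 2 reads: "To analyze the injury incidence of ACL among players with DKV in both groups". The main objective, the PICO question and the hypothesis are also about ACL injury.

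The Study variables and measurements section provides an Excel table for the "number of injuries produced among the players of both groups at the end of the study and the frequency of weekly training". Other parts of the plan touch on exposure, but none covers matches:

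- The recruitment survey (Intervention section) asks about training frequency and rest.
- A balancing rule covers training only: "The physical trainers will have to agree so that the training load in both groups is very similar".
- For adherence, "compliance with the proposed protocol will be verified through weekly self-reported questionnaires".

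The Statistical analysis section says of qualitative variables: "For these variables, hypothesis tests will be performed using the Chi-squared test". It gives Mann-Whitney or ANOVA for quantitative variables. No rate or person-time analysis is described.

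The Introduction reports injury incidence per hour at risk, separately by setting: "from 1.1 to 3.1 injuries per 1000 hours of training and from 12.6 to 23.6 injuries per 1000 hours of play".

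**The concern.** By the plan's own background figures, an hour of match play carries several times the injury risk of an hour of training. The one exposure item recorded is training frequency, which is about three sessions a week in both arms. It says little about how long a player was at risk and nothing about matches. A regular starter and an unused substitute look the same in the data.

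Match time could well differ between arms. The Randomization and blinding section allocates whole teams by coin toss, so fixtures, rotation and selection belong to the arm. Only players who screen positive for DKV are enrolled, so each arm may be a subset of its squad with its own mix of starters and reserves. If match time differs, the injury comparison absorbs the difference. With the listed data, nobody could show that this had happened or correct for it.

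**Working it through.** **The plan's own figure.** The sample size reproduces: 2 × (1.960 + 1.282)² / 1² = 21.01, rounded up to 22 per arm and 44 in total. It rests on a difference in means, so it neither uses nor is changed by exposure time. It matters here because 22 per arm is also the stated squad size (Participants section).

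**Inputs from the documents**
- Training rate: 1.1 to 3.1 per 1000 h; match rate: 12.6 to 23.6 per 1000 h (Introduction; all injuries).
- Training: three one-hour sessions a week for 12 weeks = 36 h (Participants and Intervention sections).
- Squad: 22 players per club.

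**Assumptions (not in the documents)**
- One 1.5 h match a week for 12 weeks, so a full-time starter plays 18 h; 11 players on the pitch.
- Equal fixtures at both clubs, and no programme effect.
- The match-to-training pattern for all injuries also holds for ACL injuries.

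**Step 1: relative hazard.** 12.6/3.1 = 4.1 and 23.6/1.1 = 21.5.

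**Step 2: whole squads enrolled.** Mean match time = 11 × 18 / 22 = 198/22 = 9 h at both clubs, whoever starts. There is no bias. Matches are then 9/45 = 20% of hours, but between 113.4/(111.6 + 113.4) = 50% and 212.4/(39.6 + 212.4) = 84% of expected injuries.

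**Step 3: 18 of 22 enrolled at each club.**
- All four omitted players are full-time starters: (198 − 72)/18 = 7 h.
- All four are reserves who never play: 198/18 = 11 h.
- Three starters and one reserve: (198 − 54)/18 = 8 h. The reverse: (198 − 18)/18 = 10 h.

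**Step 4: apparent effect.** Count ratio = (36 × training rate + lower match hours × match rate) / (36 × training rate + higher match hours × match rate).

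| Training, match rate | 7 v 11 h | Apparent reduction | 8 v 10 h | Apparent reduction |
|---|---|---|---|---|
| 1.1, 12.6 | 127.8/178.2 = 0.72 | 28% | 140.4/165.6 = 0.85 | 15% |
| 3.1, 23.6 | 276.8/371.2 = 0.75 | 25% | 300.4/347.6 = 0.86 | 14% |
| 1.1, 23.6 | 204.8/299.2 = 0.68 | 32% | 228.4/275.6 = 0.83 | 17% |
| 3.1, 12.6 | 199.8/250.2 = 0.80 | 20% | 212.4/237.6 = 0.89 | 11% |

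If the intervention arm is the one with more match time, the 7 v 11 h ratio is 1.25 (250.2/199.8) to 1.46 (299.2/204.8), which would hide a benefit. Extending the window to 16 weeks at the same weekly hours leaves these ratios unchanged.

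**Step 5: would combined hours be enough?** At 7 v 11 h the total hours are 43 v 47. The combined rate ratio is the count ratio × 47/43: from 0.6845 × 1.093 = 0.75 to 0.7986 × 1.093 = 0.87. A spurious reduction of 13% to 25% remains. Within match and training strata, each expected ratio is 1.0.

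**Step 6: expected ACL events.** With 22 players averaging 9 h, injuries of all types per arm are 22 × (39.6 + 113.4)/1000 = 3.37 to 22 × (111.6 + 212.4)/1000 = 7.13. Applying the Introduction's 16% to 32% ACL share gives about 0.5 to 2.3 ACL injuries per arm over 12 weeks.

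**The case against.** A reader might infer that the missing match time would itself produce something like the 51% reduction cited in the Justification for the study. An arm averaging 18 h of match play against one averaging 9 h does give 34% to 46% fewer injuries with no programme effect. The documents do not support that scenario. An 18 h mean needs an arm of at most 11 players, all full-time starters, whereas the plan seeks 22 or more per arm from 22-player squads. The 51% is also a figure for ACL injury, while the calculation uses rates for all injuries.

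A reader might also infer that incidence cannot be calculated at all. That goes too far. The PICO question and hypothesis speak of risk, and injured players divided by enrolled players is a legitimate cumulative incidence that the listed data support. Clubs might also be able to supply hours afterwards from their own records. The plan does not adopt the Introduction's hourly definition for objective 2, and it does not say that injury counts are among the variables tested by Chi-squared.

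It is also fair to say that so few ACL injuries are expected that neither a real effect nor a spurious one is likely to reach significance, and that one team per arm is the larger weakness.

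These points limit the size of the concern but do not remove it. A cumulative incidence is still affected by match time if the arms differ in it, and a small event count makes an imbalance harder to see.

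**Conclusion.** The point holds as a worthwhile, inexpensive improvement. In the available text, the listed data omit the setting with the higher hourly injury rate. The two clubs could differ in match time among enrolled players, and such a difference could neither be detected nor adjusted for.

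The size is unknown and the direction could be either. Under the stated assumptions it is nil if whole squads are enrolled. If 18 of 22 are enrolled per club, it is about 11% to 17% at 8 v 10 h and at most about 20% to 32% at 7 v 11 h; smaller enrolled subsets allow more. The documents give no match hours and no expected number of DKV-positive players, so these are illustrations and not estimates. The conclusion also depends on the annexes, including the schedule in Annex III, not already providing for match time.

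**What to change.** Add two columns to the existing Excel table, filled weekly for every player in both arms: match minutes and training minutes. Cover the whole period over which injuries are counted, including the 4 weeks after completion if the count runs to the last measurement. Stop a player's exposure at ACL injury or withdrawal. Record for each injury whether it occurred in a match or in training.

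In the Statistical analysis section, state that ACL injuries will be reported per 1000 h, separately for match and training, with exact Poisson intervals, alongside the proportion of players injured. Compare arms with a rate ratio stratified by match and training, not on combined hours alone. Say in advance what will be reported if an arm has no events.

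The cost is a few minutes of data entry per club per week and a sentence or two in each of the two sections. The intervals will be wide because few ACL injuries are expected. The change does not cure the confounding of programme with club that comes from having one team per arm.

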5. To analyze the perceived satisfaction rates of the athletes, using the SF-12 questionnaire after the intervention.
6. Know the effective dosage of a specific protocol for the prevention of ACL injuries.

PICO Question

In soccer players with DKV... Does a specific training protocol reduce the risk of ACL injuries compared to the conventional program?

Study hypothesis

A comprehensive and specific 12-week training protocol for the 2023-2024 season will significantly reduce the risk of ACL injuries compared to conventional training for female soccer players with DKV.

METHODOLOGY

Ethical documents and prior registration

This study has the Authorization of the Ethics Committee of the Responsible Research Office of the Miguel Hernández University of Elche for the 2022/2023 academic year and will be registered as a clinical trial in the clinicalTrials platform.

Studio Design

The study is designed as a randomized and controlled, double-blind, unicentric and parallel group clinical trial protocol that will be carried out with the female players of Elche CF and Intercity CF in the province of Alicante. The recommendations of the SPIRIT guide³⁶ have been followed for the realization of this study. Annex I.

Before starting the study, they will be provided with a written informed consent that they must sign to record their intention to participate in it, being able to revoke it at any time and accepting the conditions that will appear in the document (Annex II). They will be randomly assigned to a conventional fitness training program or a specific training protocol for 12 weeks. This study will consist of 3 time measurement points, the first prior to the intervention, the second at the end of the 6-week period of intervention and the last at 4 weeks after its completion. The study schedule and flowchart are in Annex III and IV, respectively.

Participants

The recruited population will be formed by the 44 elite players (22 per team) with a federative record belonging to the first senior team of Elche CF and Intercity CF of the province of Alicante of the national women's football league during the 2023-2024 season, where three weekly training sessions of one hour each are carried out. Prior to the collection of data, permission will be requested from the Club and the coach of both teams to carry out the study at the Martínez Valero Stadium in Elche. In the same way,

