This clinical trial protocol seeks to encourage coaches of women's soccer teams to follow this type of program because of its potential benefits in preventing ACL injuries. Annex X. Almost all the studies reviewed confirm that there are varied prevention programs (plyometrics, balance, strength, among others) that provide a significant improvement in DKV and, therefore, in the prevention of ACL injuries, but none of them has been based on a standard dosage or applied specifically to female footballers in this age range who have the highest injury rate^{5,14,19,21,34}. On the other hand, studies such as Willadsen et al.³¹ report short-term benefits and intervention programs that do not exceed 6-8 weeks of training¹⁴. The purpose of this study is to implement a standardized protocol for a period of 12 weeks (longer intervention time) in players of senior women's teams with the aim of achieving long-term benefits.

Limitations

- The study will be carried out only with female footballers of a specific age range, so that, when extrapolating the results, data such as the prevalence of ACL injuries could not be generalized to the entire population, so it would reduce external validity.
- We would not have all the control over the execution of the exercises described in the protocol, since the physiotherapists in charge of giving instructions would not be constantly controlling how each player performs the exercises, only at the beginning of the program or when introducing new exercises.

- To properly quantify the load, it might be more appropriate to do so with an accelerometer. It would serve to better control the exercise since, when the speed decreased, it would be indicative of stopping the exercise.
- As in almost any study, there is a risk of abandonment of the subjects, which increases with the duration of the study. Being a 12-week intervention, dropout rates could be higher.
- The relationship of the menstrual cycle in female footballers could be considered throughout the protocol, since there could be alterations in the performance and execution of the exercises¹¹.

Strengths

- Observer bias will be mitigated because measurements will be performed by two different physiotherapists. Both will not know the results of the other measurements made to prevent their expectations from influencing the result.

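### The stated sample size of 48 women cannot be reached from two squads of 22, so the 90% power has no dropout reserve behind it

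*Combined protocol and SAP*

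**What the plan says.** All of the relevant text is in the Methodology part of the combined protocol and SAP.

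- **Sample size.** The inputs are "a standardized mean difference of 1, a significance level of 0.05, a 95% CI and a power of 90% will be considered". The number of evaluable players derived from these inputs is given next: "which determines a total sample size of 44 subjects, 22 in each group". The plan then adds 10% for abandonment and concludes: "Therefore, the total sample size will be 48 women, 24 in each study group".
- **Participants.** "The recruited population will be formed by the 44 elite players (22 per team"), drawn from the first senior teams of two named clubs.
- **Intervention.** Recruitment is confined to those clubs: "an invitation will be made to all the players who are part of the teams mentioned above". After the survey there is a visual drop vertical jump screen, and "only those who test positive for DKV can be registered".
- **Randomization and blinding.** "Teams will be randomly assigned to one of the two groups in a simple manner", by the toss of a coin.
- **Limitations.** On loss to follow-up: "Being a 12-week intervention, dropout rates could be higher".

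No third team, reserve squad or replacement rule is mentioned.

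**The concern.** The enrolment figure and the source population disagree in the current text. The number available before screening (44) equals the number of evaluable players that the calculation requires, so the players meant to absorb dropout do not exist.

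Two things are at stake. First, the trial would have to be reported as under-recruited against a target that it could not have met. Second, the plan attaches 90% power to the trial without conditions. A non-significant result would then be read as coming from a trial with 90% power, when that holds only with no loss at screening, consent or follow-up.

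**Working it through.** **Inputs.** Standardized mean difference (SMD) 1, alpha 0.05, power 90%, 1:1 allocation and 10% dropout come from Sample size. Two-sided testing comes from Statistical analysis. The pool of 2 × 22 players comes from Participants, and allocation by team from Randomization and blinding.

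**Step 1: reproduce the plan's figure.** By the normal formula for two independent means,

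n per group = 2 × (1.9600 + 1.2816)² / 1² = 21.01, rounded up to 22, so 44 in total.

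Inflation: 44 × 1.10 = 48.4, stated as 48 (24 per group). Dividing by 0.90 instead gives 48.9, which is close. The arithmetic in the Sample size section is therefore sound, and the 44 is the number of *evaluable* players.

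**Step 2: compare with the source.** Pool: 2 × 22 = 44, against 48 required, a shortfall of 4. Per arm, under team allocation: 22 against 24, a shortfall of 2. The age, experience and injury criteria, the DKV screen and refusals can only widen the gap.

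**Step 3: power at the numbers that can occur.** For a two-sample t-test with arms n₁ and n₂ and SMD 1, the noncentrality is √(n₁n₂/(n₁+n₂)) on n₁+n₂−2 degrees of freedom. At 22 per arm it is √(484/44) = 3.317; at 20 per arm it is √(400/40) = 3.162.

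| Evaluable total | Arms | Power, t-test | Power, normal formula |
|---|---|---|---|
| 48 (as stated, no loss) | 24 + 24 | 92.4% | 93.4% |
| 44 | 22 + 22 | 89.97% | 91.3% |
| 43 | 22 + 21 | 89.3% | 90.6% |
| 42 | 21 + 21 | 88.5% | 89.98% |
| 40 | 20 + 20 | 86.9% | 88.5% |
| 36 | 18 + 18 | 83.0% | 85.1% |
| 34 | 17 + 17 | 80.7% | 83.0% |
| 33 | 17 + 16 | 79.4% | 81.9% |
| 30 | 15 + 15 | 75.3% | 78.2% |

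The plan's own 10% loss applied to 44 leaves 44 × 0.90 = 39.6, about 40. At 20 per arm the SMD detectable with 90% power is 1.05.

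**Step 4: illustration only.** The documents do not give the share of players who will be eligible and DKV-positive. The shares below are assumptions. They are combined with the plan's 10% dropout, and arm sizes are left unrounded.

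| Assumed eligible share | Evaluable per arm | Power, t-test | SMD detectable at 90% |
|---|---|---|---|
| 80% | 22 × 0.8 × 0.9 = 15.84 | 78% | 1.19 |
| 60% | 22 × 0.6 × 0.9 = 11.88 | 64% | 1.39 |
| 50% | 22 × 0.5 × 0.9 = 9.9 | 56% | 1.54 |

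Every value in both tables treats players as independent. With one team per arm, all of them are upper bounds.

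**The case against.** **The 44 might be a recruitment target, not the squad size.** It matches the uninflated calculation exactly, and the Intervention section invites all players of the teams without giving a number. The annexes with the flowchart and the sample size calculation are not in the available text. This reading is possible but strained: the Participants section speaks of a definite set of 44 players, 22 per team, belonging to the first senior teams. Even on this reading, 44 and 48 conflict and must be reconciled.

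**The cap of 22 per arm depends on allocation by team.** The Studio Design section can be read as randomizing individual players. On that reading the cap per arm goes, but the ceiling of 44 stays and 48 is still out of reach.

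**The statement that 90% holds only with no loss depends on the method.** This is correct as far as it goes. By the normal formula, one lost player leaves 90.6% and one per arm leaves 89.98%. By the t-test, 22 per arm gives 89.97%, which is 90% only after rounding. The t-test is the better reference because the planned comparison of normally distributed outcomes is an ANOVA between two groups. The two methods differ by about 1 to 3 points in the first table.

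**The 80% threshold needs near-equal arms.** This stands. If all losses fall in one team, 22 + 13 (9 lost) already gives 79.2% by the t-test. By the normal formula, 17 + 16 still gives 81.9%.

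**The loss shown by the plan's own figures is modest.** This also stands: 4 players and about 3 points of power. The larger falls rest on assumed eligible shares. The need for correction comes from an enrolment figure that is impossible as written and a power statement with no condition attached, not from the size of that fall.

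**Conclusion.** The concern holds and the text must be corrected. The total of 48 is 4 more than the whole source population, and the dropout reserve cannot be filled. The 90% power (89.97% by the t-test) requires all 44 squad members to be eligible, DKV-positive, willing and retained. Under the plan's own 10% dropout it is at most 86.9% by the t-test (88.5% by the normal formula). With near-equal arms, the t-test power drops below 80% when 11 of the 44 are lost.

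This rests on reading the 44 as the full pool, on allocation by team for the cap per arm, and on independent players. The last assumption favours the plan.

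**What to change.** In the Sample size section:

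1. Replace the total of 48 with all eligible and consenting players from the 44, at most 22 per group. If the squads are in fact larger than 22, state their size and reconcile the two sections on that basis.
2. Replace the unconditional 90% with a conditional statement: for an SMD of 1, power is at most about 87% by the two-sample t-test if all 44 are enrolled and 10% are lost (about 40 evaluable), and an SMD of 1.05 is detectable with 90% power.
3. State that power and the detectable SMD will be recalculated from the number of players in each team who pass the DKV screen, before the intervention starts.
4. Label these values as upper bounds that assume independent players, since each arm is one team.

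Do not enter an assumed eligible share as an expected figure, because the documents offer no basis for one.

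The cost is one paragraph and one recalculation after a screen that is already planned. No extra players are needed. The downside is a less favourable stated power.
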